Outcome: Measured variables at enrollment – with REDCap, which will take approximately 20 minutes to fill out:

Demographic Questionnaire:

- Age
- Sex
- Ethnicity
- Race
- Marital status
- Education
- Current work status
- Current or previous occupation
- Hand dominance

Primary outcome:

- Decision conflict scale (DCS) – quantifies the state of uncertainty about a course of action.
- 11-point ordinal satisfaction scale – quantifies the satisfaction with overall treatment.
- 11-point ordinal satisfaction scale – quantifies the satisfaction with decision-making.

Secondary outcome

- Knowledge questionnaire
- Stage of decision making
- Decision Self-efficacy Scale
- Acceptability (Cohort 1 will not receive this questionnaire)
- Pain Self efficacy Questionnaire (PSEQ)
- 9-item Shared Decision Making Questionnaire (SDM-Q-9)

Primary health outcomes variables:

- Quick-DASH
- EQ-5D

At follow-up 1 week-1 month and 6 months after enrollment we will have patients complete the following online REDCap questionnaires, which will take approximately 20 minutes:

The decision-making process variables:

- Quick-DASH
- PROMIS Upper Extremity CAT
- DCS
- 11-point ordinal satisfaction scale – quantifies the satisfaction with overall treatment and decision-making.

- 11-point ordinal satisfaction scale – quantifies the satisfaction with decision-making.
- Decision Regret scale (measures distress or remorse after a health care decision)

VI. BIOSTATISTICAL ANALYSIS

Statistical issues

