Based on previous studies, scores of 25 or lower on the DCS (0-100) are associated with low decisional conflict and following-through with decisions.¹⁵ On the other hand, scores of 39 or higher are associated with heightened mental conflict resulting in a delay in the decision making.¹⁵ Our study will measure the rate of patients having a conflict in decision-making. A sample size of 126 total patients was chosen to measure our primary outcome with 80% power, 0.5 effect size and an alpha of 0.05. Chi-square tests will be conducted to determine the differences between two categorical variables. Independent Student's t-tests will be performed to determine the differences between continuous and dichotomous variables. Paired samples T-test will be used to compare the mean scores for the same group on different occasions. Pearson's correlation or Spearman correlation will be used to explore the strength of the relationship between the conflict of decision-making and the use of decision aids. Wherever the minimum expected cell frequency is less than five, the Fisher's exact test will be used instead of the Pearson's Chi-square test. All variables with significant ($p < 0.05$) or near significant ($p < 0.08$) relationships will be evaluated with backwards multivariate/binary logistic regression (depending on the outcome variable) Descriptive statistics will be summarized in terms of means, standard deviations or frequencies, and will be calculated at each time point. Incomplete data will be adequately described and mean imputation will be used when deemed necessary. We will use IBM SPSS ® (19) to perform the data analysis.

VII. RISKS AND DISCOMFORTS (Stratify by common and uncommon)

The greatest discomfort associated with participation is the time required to fill out the decision aid and complete the questionnaires. Completing the DA will require approximately 20

minutes, but this can be done at home. The Questionnaires will require approximately 20 minutes at the time of enrollment.

VIII. POTENTIAL BENEFITS

Individuals managed without a DA will not experience any additional benefits, but will also not have any extra risks. Patients managed with a DA, on the other hand, may experience less decisional conflict and improved knowledge about their disease. The study will benefit society as a whole by providing a better understanding of the factors that influence patient decision-making and surgical outcomes for orthopedic problems.

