Subjects will not receive monetary remuneration for their participation in this study. Since the patients have to return to the Hand and Upper Extremity Service for their regularly scheduled follow-up and the questionnaires are being sent online via REDCap, there are no additional monetary costs associated with participation in this study.

IX. MONITORING AND QUALITY ASSURANCE

Patients are not obligated to answer any questions. The patient's participation will not affect their medical care. Patients can withdraw from the study at any time. Patients who are disturbed by any of the questions will be offered psychological counseling, referral to a psychiatrist, or immediate transfer to the emergency room for psychiatric evaluation, depending upon the severity of the reaction.

Study physicians will be readily accessible for consultation should a study patient experience increasing discomfort while completing the questionnaire.

In the unlikely event that a patient has a severe adverse emotional disturbance while completing the questionnaire, we will contact the Acute Psychiatric Service and immediately take the patient to the Emergency Department for treatment. Subjects transported to the Emergency Department for additional care will not be asked to complete the questionnaires and will be dropped from the study.

Adverse events are defined as harmful occurrences to study participants, either study related or non-study related. These events may include an exacerbation of a pre-existing illness, increase in frequency or intensity of pre-existing episodic event or condition, condition detected or diagnosed even though it may have been present prior to the start of the study, or the worsening of the disease or symptom that was present before study participation. As a result of participant self-report, study staff discovery, or routine study assessments, the study staff may become aware of an adverse event. Fluctuations in depressed mood (that do not involve suicidality) are not considered adverse events.

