questions based on the previous answer. In other words it adapts. Answering questions which are not applicable to a patient's situation might seem unnecessary to patients, which results in a higher chance of questions being left blank, which in turn results in missing data. With the IRT answering technique it is less time consuming to complete questionnaires and thus more patient friendly. Missing questions are encountered frequently and with this technique patients do not need to complete questions which they think are irrelevant. Measures within the REDCap library can be included as well as custom instruments created or entered by the researcher. Patients can log in to complete online questionnaires. When no electronic medium (e.g., computer, laptop, Ipad) is available, we will collect the data through the paper version of the measurements (any PROMIS measure can also be downloaded for administration on paper), and afterwards enter the collected data into the REDCap.

REDCap enables customization of item or instruments (e.g., format, randomization, skip patterns), storage of protected health information in a separate, secure database, automated accrual reports, real-time data export, among many other features. REDCap is well secured and effectively protected and a compliant application which includes databases which store confidential, personal health information.

Questionnaires and self-reported responses will not become part of the patient's medical record and will not contain medical record numbers or names. Hardcopies of study related data and forms will be stored in a lockable file cabinet. Patient information will remain confidential by keeping identifying information (name, medical record number, and subject number) in a separate locked file cabinet. Only the investigators and study staff specified on the consent form will have access to this information.

Any magnetic or electronic information will be saved in Partners password-protected computers to which only research coordinator and persons involved with the research project will have access.

REFERENCES:

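### Section VI permits mean imputation without saying which mean, at what level or on what trigger, so whole missing follow-up scores could be filled

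*Combined protocol and SAP*

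**What the plan says.** Section VI (Biostatistical Analysis) covers missing data in one sentence: "Incomplete data will be adequately described and mean imputation will be used when deemed necessary". No other section says which mean is meant, whether the unit filled is an item or a whole score, how much missingness prompts filling, or who decides.

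Other sections bear on what could be missing:

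- **Items.** Section IX discusses blank questions when it explains adaptive testing. It refers to a "higher chance of questions being left blank, which in turn results in missing data" and adds "Missing questions are encountered frequently".
- **Whole scores.** Section IX also says "Patients are not obligated to answer any questions" and "Patients can withdraw from the study at any time". Section V has later assessments completed online: "At follow-up 1 week-1 month and 6 months after enrollment we will have patients complete the following online REDCap questionnaires". Those are Quick-DASH, PROMIS Upper Extremity, DCS, satisfaction and decision regret.
- **Enrollment DCS.** Section V has it completed at the visit, after randomization.
- **Binary use of the DCS.** Section VI states "Our study will measure the rate of patients having a conflict in decision-making", but names neither the visit nor which of its two reference scores (25 and 39) is the cut-off.

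**The concern.** Mean imputation is not one method. Filling with the patient's own mean, the arm mean or the overall mean has different consequences, and so does filling an item as against a whole score. The sentence permits all of them.

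For whole scores, arm-mean filling adds records with no variability. The standard error then comes out too small and the test rejects too often. Overall-mean filling pulls both arms toward a common value and dilutes the difference. If a filled DCS is then dichotomised, every missing patient in an arm lands on the same side of the cut-off.

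The outcomes exposed are mainly the follow-up ones. These matter because satisfaction, clinical outcomes and regret are the plan's second aim, and regret and PROMIS Upper Extremity are listed only at follow-up. With the trigger left to judgement, the choice of method could also be made after results are known.

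**Working it through.** **Inputs.** From Section VI: 126 patients in total, 80% power, effect size 0.5, alpha 0.05, independent t-tests for continuous scores. Assumed: 1:1 allocation, two-sided testing, SD = 1, and a fraction m of whole follow-up scores missing completely at random, equally in both arms. The documents give no missing rate, so m = 10/20/30% is only a range.

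**The plan's own figure.** n per arm = 2(1.960 + 0.842)² / 0.5² = 62.8, so 63 per arm and 126 in total. This reproduces the stated size exactly.

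**Arm-mean filling of whole scores.** The true standard error is √(2/[63(1 − m)]). The reported one is smaller by a factor of about (1 − m). At m = 20% the true value is √(2/50.4) = 0.20 and the reported value about 0.8 × 0.20 = 0.16 (0.159 in simulation). Type I error is about 2[1 − Φ(1.96(1 − m))], which gives 7.8/11.7/17.0%.

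**Overall-mean filling of whole scores.** Each filled arm mean is (1 − m) × observed mean + m × overall mean, so the estimated difference is (1 − m) × 0.50 = 0.45/0.40/0.35. The reported standard error shrinks in step with the estimate, so type I error is held, but the interval is centred in the wrong place.

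Simulation (40,000 replicates per cell) agrees with both:

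| | 10% missing | 20% missing | 30% missing |
|---|---|---|---|
| Arm mean: type I error | 8.0% | 11.8% | 17.4% |
| Arm mean: 95% CI coverage | 92% | 88% | 83% |
| Overall mean: type I error | 5.1% | 5.1% | 5.1% |
| Overall mean: estimate of a true 0.50 | 0.45 | 0.40 | 0.35 |
| Overall mean: 95% CI coverage | 94% | 90% | 82% |
| Observed scores only: type I error | 5.1% | 5.1% | 5.1% |
| Observed scores only: power | 75% | 70% | 64% |

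Under arm-mean filling, apparent power stays at 81–83%, which hides the loss of information shown in the last row.

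**Skipped items.** Simulation with 63 per arm, assuming a 16-item scale with inter-item correlation 0.5 and 5/10/20% of items skipped at random (4,000 replicates, so about ±0.7 points of Monte Carlo error):

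- Full data: type I error 4.9/5.6/5.0%.
- Patient's own scale mean: 4.8/5.7/4.5%, power 78–79%.
- Overall item mean: 4.9/5.6/4.8%.
- Arm-specific item mean: 6.0/8.8/11.8%. Repeat simulations put this at about 6–7/7–9/12%.

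**Dichotomised follow-up DCS.** Assume normal scores with SD 20, cut-off 39, 20% missing and arm-mean filling. The true rate is p = 1 − Φ((39 − mean)/20), and the filled rate is 0.8p, plus 0.2 if the arm mean is at or above 39.

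| Arm mean | True rate | Filled rate |
|---|---|---|
| 20 | 17.1% | 13.7% |
| 30 | 32.6% | 26.1% |
| 45 | 61.8% | 69.4% |

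For means of 20 and 30, the between-arm difference falls from 15.5 to 12.4 points. For 30 and 45 it rises from 29.2 to 43.3 points. Which happens depends on whether the arm means straddle the cut-off. The normal model is rough (mean 20 with SD 20 puts 15.9% of patients below zero on a 0–100 scale), so these figures show direction rather than size.

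**The case against.** The strongest reply is that the sentence is meant for skipped items. Section IX discusses missing data only as blank questions, and filling a few items from the patient's own scale mean does no material harm. That stands as far as it goes. But Section VI does not limit itself to items or to the patient's own mean, and item filling is not safe whichever mean is used, as the arm-specific result shows.

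Second, the inflated type I error needs three things together: whole scores filled, by arm mean, with appreciable loss. The documents state none of them. This is correct, and a reader might wrongly infer that the trial will have an inflated error rate. The documents support only that the plan leaves this open. Contact by mail, phone and email (Section III), scheduled clinic follow-up (Section VIII) and paper forms (Section IX) should also limit the loss, although they do not define the rule.

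Third, a reader might infer that the enrollment DCS comparison is compromised. It is not, to any extent that the documents suggest, because that questionnaire is completed at the visit.

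Fourth, it is tempting to cite the Section IX provision that patients taken to the Emergency Department "will not be asked to complete the questionnaires and will be dropped from the study" as a source of scores to be filled. On its plain reading it describes exclusion, so it does not support this point.

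Finally, the plan does not say that the follow-up DCS will be dichotomised. The binary result is conditional on that.

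**Conclusion.** The point holds as a gap that should be closed. The plan names mean imputation as its only way of filling missing values, leaves the mean, the level and the trigger undefined, and does not exclude whole follow-up scores. The omission itself is certain.

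Its size is conditional on a missing rate that the documents do not give. Over 10–30% of whole scores missing completely at random, the consequence runs from false positives (type I error of about 8–17%) under arm-mean filling to dilution (0.50 SD read as 0.45–0.35) under overall-mean filling. If only isolated items are filled from the patient's own mean, the effect is negligible.

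Nothing in the documents shows an intention to choose the method after seeing results; the wording simply does not prevent it. The sample size of 126 is not in dispute here.

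**What to change.** Amend Section VI as follows:

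1. Delete mean imputation of whole scores and the discretionary trigger. Analyse observed scores in the randomized arms.
2. Fill only isolated skipped items, using the patient's own mean on that scale, up to a limit on skipped items fixed before data are seen. Do not use an arm or sample mean.
3. Do not dichotomise a mean-filled DCS.
4. Make the promised description of incomplete data concrete by reporting the number missing by arm and visit.

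A likelihood-based repeated-measures model for scores collected at several visits is an optional preference. It can draw on enrollment values for the DCS, satisfaction and Quick-DASH, but not for regret or PROMIS Upper Extremity, which are not listed at enrollment.

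The cost is a short paragraph. Intervals will be wider than under arm-mean filling, because they will reflect the information actually collected. The observed-score comparison still assumes data missing completely at random, and the report should say so.

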**A randomized trial measuring the effect of
Decision Aids on patients' satisfaction,
conflict of decision-making and clinical
outcome.**

NCT03181724

Version Date of the Document: 16 September 2016

PARTNERS HUMAN RESEARCH COMMITTEE DETAILED PROTOCOL

A randomized trial measuring the effect of Decision Aids on patients' satisfaction, conflict of decision-making and clinical outcome.

DETAILED PROTOCOL

VERSION 9/16/2016

PI: [name]

I. BACKGROUND AND SIGNIFICANCE

Decision aids are tools that help patients participate in making decisions by providing detailed, specific, and personalized information regarding the benefits and risks of various potential treatment options for a diagnosis. Decision aids can reduce the level of uncertainty and mental anguish associated with choosing a particular course of action, i.e. '**decisional conflict**'.¹ The most common manifestations of decisional conflict include verbalized uncertainty about choices or undesired consequences of alternatives, vacillation between choices, and delayed decision making.

Patient decision aids or "shared decision making programs" are interventions meant to prepare patients to make better or more informed decisions about their health care. By being involved in the decision-making process, patients can have a greater understanding of the risks and benefits of treatment options and the ability to make well-informed choices. In order to do this, however, patients need adequate, clear, and balanced information. Based on research in other fields, decision aids have been shown to decrease decisional conflict increase confidence with decisions, increase knowledge and may improve satisfaction with the process of decision making and the overall treatment outcome.² Decision aids have also been shown to have positive effects on shared decision making.³

A Cochrane systematic review of 86 randomized control trials (RCT's) evaluating patient decision aids (largely in medical subspecialties) showed that these tools increased patients'

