All patients will be randomized to either a cohort managed with a decision aid (Cohort I) or to a cohort managed without a decision aid (Cohort II). A research fellow does the randomization after the first consult at the outpatient clinic with a computer generated simple randomization sequence.

V. STUDY PROCEDURES

This study will employ a randomized, prospective design. The baseline data are gathered at enrollment. The patients will be randomly assigned to two different cohorts after the encounter with the physician. The physician will be informed that the patient is participating in this study, but will not know to which cohort the patient will be randomized.

Cohort I will be managed with standard care plus a decision aid (henceforth “DA”), and cohort II will be managed without one. The patients in Cohort I will receive the DA, which they can complete in a separate room and take home. The decision aids include information on the disease/condition, treatment options, benefits, risks, scientific uncertainties, and probabilities of potential outcomes tailored to the patient’s health risks factors. Additionally, it includes values clarifications such as describing outcomes in functional terms, asking patients to consider which benefits and risks matter most to them, and guidance in the steps of decision making and

discussing their decision with family/friends. It is interactive and dynamic, helping patients clarify their preferences and come to a decision that feels best to them.

Cohort II will receive the standard care including—at the surgeon’s discretion—the American Society of Surgery of the Hand (ASSH) informational brochure. The patients will have the opportunity to read the brochure in a separate, quiet room or take it home. The ASSH - brochure contains anatomic illustrations of the injury and a discussion of surgical and non-surgical treatments for the diseases, and a general description of expected outcomes. Similar to the patients in cohort II, the patients in cohort I can read and complete the DA in a separate quiet room and take the decision aid home.

After randomization all patients will complete the REDCap questionnaires about the conflict in decision-making, which will take approximately 20 minutes. After completing the study procedures, the physician will return to the room and continue with the visit with the patient. The visit will be timed by a member of the study staff.

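### Section IX removes from the trial any patient taken to the Emergency Department; after randomization this is an exclusion plausibly related to outcome, small in effect and cheap to correct

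*Combined protocol and SAP*

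**What the plan says.** Section IX describes what happens "In the unlikely event that a patient has a severe adverse emotional disturbance while completing the questionnaire": staff contact the psychiatric service and take the patient to the Emergency Department. It then states: "Subjects transported to the Emergency Department for additional care will not be asked to complete the questionnaires and will be dropped from the study".

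The timing comes from Section V: "After randomization all patients will complete the REDCap questionnaires about the conflict in decision-making". Section V also lists the instruments. The primary outcomes are two satisfaction scales and the "Decision conflict scale (DCS) – quantifies the state of uncertainty about a course of action". For later time points: "At follow-up 1 week-1 month and 6 months after enrollment we will have patients complete the following online REDCap questionnaires". The follow-up set includes the DCS, satisfaction, the Decision Regret scale, Quick-DASH and the PROMIS upper-extremity measure.

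Section VI gives the sample size: "A sample size of 126 total patients was chosen to measure our primary outcome with 80% power, 0.5 effect size and an alpha of 0.05". For missing data it promises a description and mean imputation where judged necessary. It defines no analysis population. Sections III and IX already let a patient decline any question and withdraw at any time.

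**The concern.** The sentence in Section IX joins two instructions. The first, not asking a distressed patient to carry on with the questionnaire, protects the patient. The second removes the patient from the trial without a request to leave. It adds no protection that the rights to refuse and to withdraw do not already give.

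The trigger is not obviously independent of what the trial measures. Section I says: "Decision aids can reduce the level of uncertainty and mental anguish associated with choosing a particular course of action". Section V describes the regret scale as a measure of distress or remorse. A patient who becomes severely upset while answering such items may well be one with high conflict or regret. The two cohorts receive different material beforehand, so the risk could differ between them, although the documents do not show that it does.

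At stake is the comparison of the groups as randomized. A patient dropped at the enrollment visit also loses every later outcome, even if that patient recovers and is willing to answer.

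**Working it through.** **1. When is this a post-randomization exclusion?** Section V gathers baseline data at enrollment, randomizes after the physician encounter, and then gives the decisional-conflict questionnaires. A disturbance during those questionnaires, or during a follow-up questionnaire, removes a randomized patient. A disturbance during any baseline collection before randomization would not.

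**2. Does other text repair it?** No section states an intention-to-treat population, retention of data already collected, or continued follow-up of these patients. Section VI offers only mean imputation.

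**3. The planned sample size.** Inputs from Section VI: effect size 0.5, alpha 0.05, power 80%. Assumptions: two-sided test, equal allocation, and 0.5 read as a standardized mean difference.

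n per arm = 2 × (1.960 + 0.842)² / 0.5² = 62.8, rounded up to 63, or 126 in total. This reproduces the plan's figure. An exact t-test calculation gives 64 per arm, and 79.5% power at 63.

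**4. Shift in one arm's mean.** Let k patients be dropped from an arm of 63, scoring on average z SD above those who remain. If the remaining patients have mean μ, the full arm has mean

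[(63 − k)μ + k(μ + z)] / 63 = μ + kz/63.

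Dropping them lowers the observed mean by kz/63. The documents give neither k nor z, so both are assumptions:

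| k dropped (share of arm) | z = 1 | z = 2 | z = 3 |
|---|---|---|---|
| 1 (1/63 = 1.6%) | 0.016 SD | 0.032 SD | 0.048 SD |
| 3 (3/63 = 4.8%) | 0.048 SD | 0.095 SD | 0.143 SD |

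At z = 2 these are 0.032/0.5 = 6% and 0.095/0.5 = 19% of the planned effect.

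**5. On the rate scale.** Section VI also speaks of the rate of patients in conflict. If that rate is p in an arm of 63, dropping one patient who is in conflict lowers it by (1 − p)/62, at most 1.6 percentage points.

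**6. Mean imputation.** Giving dropped patients the average of those who stayed in their arm returns μ. The whole shift kz/63 remains.

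**7. Direction.** With k₁ dropped from Cohort I and k₂ from Cohort II, and the same z in both, the observed difference (I minus II) is off by (k₂ − k₁)z/63. Equal losses cancel. Losses only in Cohort I make its conflict look lower, and losses only in Cohort II do the reverse.

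**8. Power.** With 1, 3 or 6 patients lost from one arm, t-test power is 79.2%, 78.5% or 77.4%, against 79.5% with none lost. Power is not the issue.

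**The case against.** The strongest reply is that this is a rule for an event the protocol itself expects to be rare. Three emergency transfers in one arm of a hand-surgery questionnaire study, with none in the other and all three patients scoring 2 SD high, is an extreme case. The follow-up questionnaires are online, so transport by staff fits mainly the enrollment visit. Nothing in the documents shows that these patients would have the highest conflict or regret. All of this stands, and it limits the size of the point. It does not change what the rule does when it is applied.

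A second reply is that retention cannot recover an enrollment DCS that was interrupted. That is also right. What can be kept is any items already answered, the patient's place in the randomized cohort, and the later outcomes.

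A reader might go further and infer that the harm disappears from the safety record or that safety follow-up ends. The documents do not support this. Section IX defines adverse events broadly and requires those discovered to be reported to the IRB and tallied by the coordinator. Staff who take a patient to the Emergency Department have necessarily discovered the event. The sentence "Fluctuations in depressed mood (that do not involve suicidality) are not considered adverse events" would have to be stretched to cover a severe disturbance needing emergency transfer. The text does not say that adverse-event follow-up stops, or that data already collected are deleted.

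**Conclusion.** The point holds as a minor one. Section IX prescribes removal that the patient has not requested. When the disturbance arises during post-randomization questionnaires, that removal is an exclusion plausibly related to outcome, and neither an analysis-population statement nor mean imputation corrects it.

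The expected numerical effect is small. The shifts of 0.03 and 0.10 SD are illustrations, not estimates: they rest on 63 per arm, on 1 or 3 losses all in one arm, on an assumed gap of 2 SD, and on reading 0.5 as a standardized difference. A reader might infer that the rule always biases the comparison towards hiding distress. Under the assumption it lowers the observed level of conflict within an arm, but the sign of the between-arm bias is unknown.

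**What to change.** In the Section IX sentence, keep the instruction not to ask for the questionnaires and replace the clause that removes the patient from the trial. Suggested wording:

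> The patient is not asked to complete questionnaires at that time. Unless consent is withdrawn, the patient remains in the study, may be invited to the later scheduled questionnaires, and is analysed in the randomized cohort using all data collected. The number of such events is reported by cohort.

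This leaves emergency care and adverse-event reporting as written. It keeps items already answered and, for patients willing to continue, the later DCS, satisfaction, regret and Quick-DASH scores.

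The cost is a short protocol amendment and perhaps a few extra invitations. The downside is that contacting a recently distressed patient needs care, which the existing right to refuse or withdraw covers.
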